3.4 Sample Size

The sample size, up to ~96 subjects, was determined by how many subjects satisfy all inclusion/exclusion criteria when applying for participation in this study and not by any formal statistical hypothesis.

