8 CINRG DATA

8.1 Overview of CINRG Data

CINRG is a natural history registry database which collects DMD data using consortium of medical and scientific investigators from academic and research centers on neuromuscular disease. Demographics and baseline characteristics, corticosteroids medication use (and type), efficacy endpoints including 6MWT, time taken to stand from supine, time taken to run/walk 10 meters, NSAA, spirometry, and EK will be analyzed. Other endpoints collected by CINRG but not in Study 019 will not be included into this analysis plan. The CINRG natural history control will be compared to ataluren's efficacy data to assess the ataluren's long- term treatment benefit.

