8.2 Matched Populations

To compare CINRG with Study 019, the matched populations are defined in the following table for different endpoints and analyses. Matching criteria will be adjusted if imbalance demographics and baseline characteristics are observed.

Endpoint/ Analysis	Age (Years) at Study Entry	Age (Years) at Assessment	Steroid Use	Ambulation status	Exclude EXON 51 and 45	Baseline value	Visit Year
Age at loss of ambulation	9-18	Not applicable	Cumulative Steroid use duration at study entry ≥ 12 months	Ambulatory at study entry	Yes	time taken to run/walk 10 meters 3.5-26.4 seconds ²	Not applicable
Age at FVC <1 liter	9-18	Not applicable	Not applicable	Non- ambulatory at study entry	Yes	1-3.08	Not applicable
Piece-wise regression based on FVC	Not applicable	≤ 22	Cumulative Steroid use duration at each assessment ≥ 24 months	Non- ambulatory at each assessment	Yes	Not applicable	≥ 2012
%- predicted FVC	9-21	Not applicable	Not applicable	Non- ambulatory at study entry	Yes	32.6- 110.3	Not applicable
%- predicted FEV1	9-21	Not applicable	Not applicable	Non- ambulatory at study entry	Yes	28.1- 104.0	Not applicable
PEF	9-21	Not applicable	Not applicable	Non- ambulatory at study entry	Yes	1.3-218.0	Not applicable
EK	9-18	Not applicable	Not applicable	Ambulatory at study entry	Yes	Score 0-15	Not applicable
6MWT	9-18	Not applicable	Cumulative Steroid use duration at study entry ≥ 12 months s	Ambulatory at study entry	Yes	36-553 meters	Not applicable
time taken to run/walk 10 meters	9-18	Not applicable	Cumulative Steroid use duration at study entry ≥ 12 months	Ambulatory at study entry	Yes	3.5-26.4 seconds	Not applicable
time taken to stand from supine	9-18	Not applicable	Cumulative Steroid use duration at study entry ≥ 12 months	Ambulatory at study entry	Yes	2.3-30 seconds	Not applicable
NSAA	9-18	Not applicable	Cumulative Steroid use duration at study entry ≥ 12 months s	Ambulatory at study entry	Yes	Total score 3-34	Not applicable

8.2.1 Analyses Based on Matched Populations of CINRG and Study 019

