Demographics and baseline characteristics (age, race, ambulation status, corticosteroid use (yes or no), duration of corticosteroid use, corticosteroid type, baseline 6MWD, baseline time to run/walk 10 meters, baseline time to stand from supine, baseline %-predicted FEV1, %-predicted FVC, PEF, EK score, NSAA total score) will be summarized descriptively for CINRG and Study 019 based on each matched population. The summary will be displayed by corticosteroid use (yes vs no) and cumulative steroid use (≥ 12 months vs < 12 months) for baseline ambulatory and non-ambulatory subjects separately. In general, the baseline is defined as the first visit in CINRG data. The baseline age in the FVC analysis using piece-wise regression models is the age at the first FVC assessments for both CINRG and Study 019.

The comparison to the natural history data (ie, CINRG data) based on matched subjects will be performed in FVC using piece-wise regression models, age to loss of ambulation, and age to FVC < 1 liter using Kaplan-Meier method.

Piece-wise regression models will be applied to log FVC in CINRG and Study 019 data, separately, using different ages as the changepoint. The most possible changepoint in terms of age will be chosen at the best model fit (ie, AICC value is the maximal). Scatter plots of log FVC and the most fitted piece-wise regression line will be generated for CINRG and Study 019, separately. Comparison between the observed and predicted FVC in Study 019 will be performed using repeated measures analysis of variance to account for within-subject correlation, where the predicted values are based on the regression equation estimated by the best fit regression model based on CINRG data.

The Kaplan-Meier method will be applied to the analysis of age to loss of ambulation and age to FVC < 1 liter. The median age to loss of ambulation and median age to FVC < 1 liter will be reported. The comparison between Study 019 and CINRG will be conducted via log-rank test by corticosteroid use at baseline (yes or no) and overall. The Kaplan-Meier curves will also be displayed.

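### SAP 8.2.1 selects the FVC changepoint with the largest AICC, which is the worst-fitting candidate, and then tests ataluren against the resulting CINRG curve as if that curve had no sampling error

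*SAP*

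**What the plan says.** SAP 8.2.1 sets out the analysis in three steps.

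- **Model.** "Piece-wise regression models will be applied to log FVC in CINRG and Study 019 data, separately, using different ages as the changepoint". The candidate ages are not listed.
- **Selection.** "The most possible changepoint in terms of age will be chosen at the best model fit (ie, AICC value is the maximal".
- **Test.** "Comparison between the observed and predicted FVC in Study 019 will be performed using repeated measures analysis of variance to account for within-subject correlation". The source of the predictions is the fit to the natural history cohort, in the SAP's words: "where the predicted values are based on the regression equation estimated by the best fit regression model based on CINRG data".

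SAP 8.1 gives the purpose: "The CINRG natural history control will be compared to ataluren's efficacy data to assess the ataluren's long- term treatment benefit". In the matching table of SAP 8.2, the row "Piece-wise regression based on FVC" applies no restriction on age at entry or on baseline value. It limits age at assessment to 22 or below, requires at least 24 months of cumulative steroid use and non-ambulatory status at each assessment, and takes visits from 2012 onward. No alpha level, CINRG sample size or Study 019 sample size is given for this comparison. For the study overall, SAP 3.4 says the size was set "not by any formal statistical hypothesis".

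**The concern.** There are two faults, and both feed the same test.

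The first is the direction of the criterion. If the rule is programmed as written, the changepoint is the worst of the candidates, and the CINRG reference curve is wrong along much of the age range. The observed-minus-predicted difference in Study 019 then mixes lack of fit with any treatment effect.

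The second is that the CINRG predictions enter as fixed numbers. The coefficients and the changepoint are estimated from a finite sample, but nothing in the described analysis carries that uncertainty. The standard error is therefore too small and so is the p-value.

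The study is open-label with no concurrent control, and SAP Section 7 removes the paired t-tests for spirometry. This analysis and the log-rank test of age at FVC below 1 liter are the only pulmonary tests against natural history that the plan specifies.

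**Working it through.** The plan gives no figure for this analysis to reproduce, so the check is algebra followed by simulation under stated assumptions.

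**1. Direction of the criterion.** AICC = −2 log L + 2k + 2k(k+1)/(n−k−1). The candidates are fitted to the same data and differ only in the changepoint age, so n and k are constant and the penalty is the same for all. Ranking by AICC is ranking by −2 log L, which for Gaussian errors is ranking by residual sum of squares (RSS). The maximal AICC is the maximal RSS. This step needs no assumed inputs.

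One simulated data set with a true changepoint of 14 illustrates it:

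| Changepoint age | AICC | RSS | R² |
|---|---|---|---|
| 10 | 299.0 (largest) | 52.38 | 0.048 |
| 14 | 258.2 | 48.28 | 0.123 |
| 15 | 257.4 (smallest) | 48.21 | 0.124 |
| 20 | 289.5 | 51.40 | 0.066 |

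The rule as written takes age 10. Minimising takes age 15, one year from the truth.

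**2. How often the rule goes wrong.** All inputs are assumed.

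- *Set A:* 100 CINRG boys, 4 annual visits, ages 9–22, log FVC +0.05 per year to age 14 then −0.07, between-boy SD 0.30, candidate ages 10–21, 500 replicates. Minimising AICC gave a mean changepoint of 14.1 (SD 0.8). Maximising gave 10–11 or 19–21 in all 500 runs, with mean curve errors of +23% at age 10, −12% at 14, +2% at 18 and +13% at 21. Repeat runs gave 98–100% at a true changepoint of 14, and about 80% at 12.
- *Set B:* slopes +0.06 then −0.07, true changepoint 12, 14 or 16, candidates 10–20, 5 yearly visits, between-subject SD 0.30, residual SD 0.08, 50, 100 or 200 CINRG boys, 50 in Study 019, no treatment effect, 1000 replicates. Minimising came within 1 year of the truth in 97–100% of runs; maximising in 0–0.3%. With the changepoint at 14, the median largest curve error over ages 9–21 was 0.27–0.30 log units when maximising and 0.06–0.12 when minimising.

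**3. What this does to the test.** In Set B the test was represented by a one-sample t-test on subject-mean observed minus predicted log FVC, with CINRG entry ages 9–17 and a true changepoint of 14. Ranges run over 50 to 200 CINRG boys.

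| Study 019 entry ages | Bias, maximise (log units) | Type I error, maximise | Type I error, minimise |
|---|---|---|---|
| 9–17 (same mix) | about 0 | 9–18% | 8–18% |
| 11–15 | +0.038 to +0.041 | 20–23% | 8–16% |
| 9–12 | −0.011 to −0.018 | 10–25% | 9–25% |
| 14–17 | −0.023 to −0.026 | 14–26% | 10–24% |

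A bias of +0.04 is exp(0.04) − 1 ≈ 4% of FVC in favour of ataluren. A repeat with entry ages 11–15 gave about +0.06, or exp(0.06) − 1 ≈ 6%, with a type I error of 30% against 9% when minimising.

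**4. Cost of treating the prediction as known.** With equal between-subject variance and the same age mix, the variance of the difference is understated by the factor 1 + n019/nCINRG. A nominal two-sided 5% test (the level is an assumption) then has error 2[1 − Φ(1.96/√(1 + n019/nCINRG))]:

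- 45 vs 200: 1.96/√1.225 = 1.77, error 8%
- 45 vs 100: 1.96/√1.45 = 1.63, error 10%
- 45 vs 45: 1.96/√2 = 1.39, error 17%

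The Set B simulation, minimising AICC with the same age mix and 50 boys in Study 019, gave 8.4%, 9.8% and 17.6% for 200, 100 and 50 CINRG boys. The formula gives 8.0%, 11.0% and 16.6%.

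**The case against.** The reversed word is probably a slip. The sentence says the best fit is wanted, later sentences repeat that, and the required scatter plots with the fitted line could reveal a changepoint at the edge of the age range. The curve errors at single ages overstate the harm: least-squares errors largely cancel over the age range, and with the same age mix the type I error is alike under either rule. Much of the inflation therefore comes from the fixed predictions rather than from the AICC wording. The cohort sizes and simulation inputs are assumed. That the predictions are error-free is an inference from the SAP's silence. Finally, the primary endpoint is safety, the CINRG work is additional to the protocol-defined analyses, and the log-rank comparisons do not use this curve.

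Most of this stands as a limit on size. It does not rescue the rule. The SAP gives no larger-is-better form of the criterion, no other section corrects it, and SAP Section 1 makes the SAP prevail over the protocol. Relying on someone noticing a plot is not a specification. Nor can cancellation be assumed, because for this analysis the matching table restricts neither entry age nor baseline FVC.

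**Conclusion.** Both parts hold. Under the standard definition of AICC the selection rule is backwards; that follows from algebra alone. Its effect on the treatment comparison depends on the age distributions: near zero with identical mixes, about +0.04 to +0.06 log units favouring ataluren with Study 019 entry ages of 11–15, and about −0.01 to −0.03 with younger or older groups. The direction is not fixed.

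The omitted CINRG uncertainty is a separate fault, and correcting the AICC wording does not remove it. It takes a nominal 5% test to roughly 8–17% for CINRG samples from about four times the Study 019 sample down to the same size, assuming equal variances and the same age mix. With mismatched ages and small CINRG samples the simulated error was higher still.

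This is a supportive efficacy comparison and leaves the primary safety analysis untouched. The AICC rule must still be corrected before the analysis is programmed, because as written it does the opposite of what is intended.

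**What to change.** 1. In SAP 8.2.1, replace the maximal AICC with the minimal AICC, and list the candidate changepoint ages.
2. Replace the observed-versus-predicted analysis with one mixed model of log FVC on the pooled CINRG and Study 019 data, with subject random effects, cohort, age segments and cohort-by-segment terms, and test the cohort terms. If the prediction approach is kept, bootstrap CINRG by subject, repeat the changepoint selection in each resample, and carry the resulting variation into the standard error. Under the pooled model, the uncertainty from selecting the changepoint should be handled by the same kind of resampling or acknowledged in the report.

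The first change is one word plus a list of ages and has no drawback. The second is modest reprogramming of one analysis; its price is a wider confidence interval, which reflects uncertainty that is already there.

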7.2.20. Spirometry

Spirometry will be conducted in nonambulatory patients. Spirometry will be performed at Screening (Visit 1), Week 24 (Visit 4), Week 48 (Visit 6), Week 72 (Visit 8), Week 96 (Visit 10), Week 120 (Visit 12), Week 144 (Visit 14), Week 168 (Visit 16), Week 192 (Visit 18), Week 216 (Visit 20) and Week 240 (Visit 22 End-of-Treatment/Premature Discontinuation).

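### The FVC comparison with CINRG tests level rather than decline, so any FVC difference between the cohorts at entry passes in full into the estimated ataluren benefit

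*SAP*

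**What the plan says.** SAP 8.2.1 describes the FVC trajectory analysis in three steps.

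- Fitting: "Piece-wise regression models will be applied to log FVC in CINRG and Study 019 data, separately, using different ages as the changepoint". The fitted lines are plotted for each source.
- Prediction: "the predicted values are based on the regression equation estimated by the best fit regression model based on CINRG data".
- Testing: "Comparison between the observed and predicted FVC in Study 019 will be performed using repeated measures analysis of variance to account for within-subject correlation". The factors of that analysis of variance are not listed.

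In the matching table of SAP 8.2, the row "Piece-wise regression based on FVC" has no entry for age at study entry or for baseline value; its last two cells read "Not applicable ≥ 2012". It does restrict age at assessment (22 or below), steroid exposure ("Cumulative Steroid use duration at each assessment ≥ 24 months"), ambulation (non-ambulatory at each assessment), exon 51 and 45 (excluded) and visit year. The other ten rows all carry both an entry-age range and a baseline range. The companion FVC analysis, age at FVC below 1 liter, uses ages 9–18 and a baseline of 1–3.08.

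The baseline age for the piece-wise analysis "is the age at the first FVC assessments for both CINRG and Study 019". Protocol 7.2.20 limits spirometry to nonambulatory patients. Its schedule begins "Spirometry will be performed at Screening (Visit 1" and runs every 24 weeks to Week 240. SAP 8.1 states that the CINRG comparison is meant to assess ataluren's long-term benefit.

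**The concern.** The clinical question is whether ataluren slows the loss of lung function. The planned test asks something else: whether Study 019 boys lie above the CINRG line for their age. A boy whose FVC is 10% above that line at entry, and who then declines exactly as CINRG predicts, shows a 10% advantage at every visit. Allowing for within-subject correlation corrects the standard error but leaves this offset in the mean.

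The cohorts could differ at entry for reasons unrelated to the drug. Study 019 boys had to meet laboratory limits, have no uncontrolled condition and be able to attend visits (Protocol 4.2 and 4.3). SAP 8.1 describes no such requirement for the registry. What is at stake is an efficacy statement from an externally controlled comparison in a study whose primary endpoint is safety.

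**Working it through.** **1. No planned figure to reproduce.** SAP 3.4 says the sample size rests on no formal hypothesis. The documents give no alpha, sidedness, SD or number of boys for the FVC comparison.

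**2. Algebra (no assumed SDs).** Take the log scale on which the regression is fitted. For boy *i* at visit *j*, let

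log FVC = f(age) + d + τ(t) + boy effect + error,

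where f is the CINRG curve, d the cohort difference at entry, and τ(t) the effect of Study 019 dosing at time t, with τ(0) = 0.

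- Planned contrast: E[observed − predicted] = d + τ(t) at every visit.
- Anchored contrast: E[(observed − predicted at t) − (observed − predicted at entry)] = τ(t).

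With τ = 0 and d = 0.10, the planned contrast shows exp(0.10) − 1 = 10.5% higher FVC throughout, and the anchored contrast shows zero.

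**3. Does anything in the plan remove d?** Age is the regressor, so the absent entry-age criterion matters little. Restricting steroid duration, ambulation, exon and visit year narrows the populations but does not equalise FVC level. Baseline FVC is the one variable that would, and it is not restricted.

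**4. Simulation with no drug effect.** All settings are assumptions:
- 20, 30 or 50 Study 019 boys, all with a Screening value plus ten later ones
- 100 CINRG boys with five annual values
- between-boy SD of log FVC 0.25 or 0.35, within-boy SD 0.08, SD of individual slopes 0.02 per year
- CINRG line and change-point estimated in each run; 1,000 runs per setting
- two-sided 0.05 test on each boy's mean residual, counting rejections that favour ataluren (nominal 2.5%), as a stand-in for the unspecified analysis of variance

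| Entry offset d (log) | Mean estimate, level test | Level test, with Screening | Level test, post-dose only | Change from own Screening residual |
|---|---|---|---|---|
| 0 | 0.00 | 3.4–5.6% | 3.7–5.3% | 7.6–20.3% |
| 0.05 | 0.05 | 10.2–31.4% | 10.1–31.2% | 7.4–17.0% |
| 0.10 | 0.10 | 23.7–73.0% | 23.4–73.0% | 8.6–18.2% |
| 0.20 | 0.20 | 64.0–99.8% | 63.7–99.8% | 6.7–20.6% |

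A repeat under similar assumptions gave 9–25% for d = 0.05 and 22–64% for d = 0.10. Across the runs the range is therefore about 9–31% and 22–73%.

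**5. Role of the Screening value.** It is 1 of 1 + 10 = 11 scheduled values (9%). Removing it while keeping the level contrast changes no rate by as much as 1 percentage point.

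**6. Is anchoring enough?** It removes the bias: the mean estimate lies between −0.003 and +0.002 at every offset. It does not restore the error rate, which stays at about 7–21% because the test treats the estimated CINRG line as known. The estimation error of that line must enter the test as well.

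**The case against.** The strongest reply is that the plan does guard against imbalance. SAP 8.2 says the matching criteria will be revised if demographics or baseline characteristics turn out unbalanced, and SAP 8.2.1 summarises baseline %-predicted FVC for each matched population. This is partial mitigation only. There is no threshold or rule, the change would be made after seeing data, and matching on a range does not anchor individual boys. The plotted Study 019 line would let a reader look at slope, but no test of slope is planned.

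It is also fair to say that size and direction are unknown. Registry eligibility is not described, so which cohort starts higher is conjecture. The analysis-of-variance factors are unspecified, so a source-by-time term could in principle be added; the text names none.

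Three stronger readings are tempting, and the documents do not support them.

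- *The fault is counting a pre-dose value as an outcome.* Inclusion of Screening is inferred from the baseline-age definition and the lack of a post-dose restriction. The visit-year, ambulation and steroid filters may remove some Screening values, and step 5 shows they hardly matter.
- *The cohorts are unmatched.* Only baseline FVC and entry age are left open.
- *The offset precedes any treatment.* Every boy had received ataluren before (Protocol 4.2). Dosing in the earlier open-label studies stopped in March 2010 (Protocol 1.1), but a residual effect cannot be ruled out. The offset is pre-dose for Study 019, not drug-naive.

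**Conclusion.** The concern holds for the unanchored level contrast. That an entry offset passes in full into the estimate follows from the planned contrast on the log scale and needs no assumed variance. It works in both directions: a cohort that starts higher looks like benefit, and one that starts lower conceals it.

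The false-favourable rates, about 9–31% for a 5% offset and 22–73% for a 10% offset, rest on assumed numbers of boys, SDs and test form, and should be read as illustrations. The documents do not show that an offset exists. A reader might also infer that subtracting each boy's own baseline would by itself bring the test to its nominal level. It would do so only if the CINRG line were known exactly.

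**What to change.** In SAP 8.2.1, make the inferential FVC contrast one of decline.

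- Fit one joint mixed model of log FVC to CINRG and Study 019, with the age change-point, subject random effects (intercept and slope), a source main effect, time since first FVC and a source-by-time term. Base any statement of benefit on the source-by-time term. The source main effect is the entry offset.
- Equivalently, test change from each boy's own reference residual, with CINRG estimation error carried by bootstrapping both cohorts.
- Report the entry offset separately as a check on comparability, noting that boys had earlier ataluren exposure. Keep the observed-versus-predicted level comparison as descriptive only.
- Use the Screening FVC as reference where it meets the row's criteria. Report separately the boys who become eligible during the study, because their first FVC is an on-treatment value.

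The cost is SAP wording and modelling on data already collected. Intervals will be somewhat wider because the CINRG line is no longer treated as known. For boys who enter the analysis on study, the reference may absorb early drug effect. The documents do not give the number of such boys, so it should be reported.

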7.2.17. Timed Function Tests

Timed function tests will performed in those patients who are ambulatory at study entry, and include the time taken to stand from supine and time taken to run/walk 10 meters [Mendell 1989, Griggs 1991, Beenakker 2005a, Pradhan 2006] (see Study Manual). These parameters will be monitored at Screening (Visit 1), Week 48 (Visit 6), Week 96 (Visit 10), Week 144 (Visit 14), Week 192 (Visit 18) and Week 240 (Visit 22 End-of-Treatment/Premature Discontinuation).

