5.8.2 Timed Function Tests

Timed function test data (ie, time to stand from supine and time to run/walk 10 meters) and change from baseline to each post baseline visit will be summarized descriptively by visit for ambulatory subjects with non-missing baseline timed function tests assessments. Similarly the time to stand from supine and time to run/walk 10 meters will also be summarized for each actual age.

Timed function test (TFT) data imputation rules as the following will be used in the summary.

- If time to run/walk 10 meters > 30 sec, then set to 30 sec.
- If time to stand from supine > 30 sec, then set to 30 sec.

Similar to 6MWT, the time to stand from supine and time to run/walk 10 meters of will also be analyzed by means of a mixed model repeated measures (MMRM) where baseline is baseline time taken to stand from supine and time taken to run/walk 10 meters, respectively.

The Kaplan-Meier method will be applied to the analysis of age at loss of ambulation. The median age at loss of ambulation will be reported by corticosteroids use at baseline. The Kaplan-Meier curves will also be displayed. The age at loss of ambulation is defined as age of the disease progression reported as the adverse event or age at the time to run/walk 10 meters > 30 seconds, whichever occurs earlier. The subjects who are ambulatory at the end of study or discontinuation will be censored on the last valid timed function tests assessment date. Age on that date will be used in the analysis. A sensitivity analysis will be performing based on the loss of ambulation defined only by disease progression AE.

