5.8.5 Spirometry

Pulmonary function parameters of %-predicated FVC, %-predicted FEV1 (adjusted using ulna length and age), peak expiratory flow (PEF), and peak cough flow (PCF) and their absolute and relative changes from baseline will be summarized by visit for non- ambulatory subjects and As-Treated population. Similarly the observed values of the endpoints will also be summarized for each actual age.

The Kaplan-Meier method will be applied to the analysis of age at FVC <1 liter. The median age at FVC<1 liter will be reported by corticosteroids use at baseline. The Kaplan-Meier curves will also be displayed. The age at FVC<1 liter is the one at the first time FVC<1 liter. If subjects do not have FVC<1 liter, the age at the last non-missing FVC assessment will be chosen as the censor age.

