5.9.2 Corticosteroids type subgroups

The by-visit summary on the observed values and change from baseline to each post baseline visit values will be performed descriptively for each corticosteroid type prior to study entry (deflazacort vs prednisone/prednisolone) on 6MWT and TFTs. The Kaplan-Meier method will be applied to the analysis of age at loss of ambulation and age at FVC <1 liter each subgroup.

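### The age-scale Kaplan-Meier and log-rank comparison with CINRG uses no entry age, although matched boys must be event-free at entry: medians come out late, and an entry-age gap can look like a treatment difference

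*SAP*

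**What the plan says.** SAP 8.1 brings in CINRG to judge long-term benefit of ataluren. For loss of ambulation and FVC below 1 liter, SAP 8.2.1 puts age on the time axis, reports Kaplan-Meier median ages and tests the difference: "The comparison between Study 019 and CINRG will be conducted via log-rank test by corticosteroid use at baseline (yes or no) and overall". It defines the event age and the censoring age (last valid timed test, last FVC, or last report of ambulation in CINRG). It gives no age of entry into the risk set. The one planned sensitivity analysis changes only the event definition.

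The matched sets in SAP 8.2 take boys aged 9-18 at entry. For ambulation they must be ambulatory with a baseline 10-meter time of 3.5-26.4 seconds; the event is a time above 30 seconds or a report of progression. For FVC the baseline must be 1-3.08 (no unit is given; liters assumed). The section also says matching will be revised if imbalance is seen, without a measure or threshold.

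For Study 019 alone, SAP 5.8.2 says: "The Kaplan-Meier method will be applied to the analysis of age at loss of ambulation". It names no population for that curve. SAP 5.9.2 adds: "The Kaplan-Meier method will be applied to the analysis of age at loss of ambulation and age at FVC <1 liter each subgroup", and 5.9.3 does the same by steroid duration. SAP 5.8.5 says: "The age at FVC<1 liter is the one at the first time FVC<1 liter", with no minimum baseline FVC. Protocol 7.2.17 says: "Timed function tests will performed in those patients who are ambulatory at study entry".

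**The concern.** A boy who enters at 14 still walking could not have been in the matched set had he stopped walking at 12. His years before 14 carry no information about the hazard at those ages. Without an entry age, standard Kaplan-Meier and log-rank calculations still count him at risk throughout those years. Early hazards are diluted and the curve stays too high.

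This matters here because the two age windows overlap: entry is allowed from 9 to 18, and Protocol 2.1 places wheelchair dependence for most boys at 10 to 14. The medians would be read as ages at which boys stop walking, and the log-rank test as evidence on benefit. If one cohort joins older, part of any difference between the curves is only that.

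**Working it through.** **No plan figure to reproduce.** SAP 3.4 has no power calculation: "The sample size, up to ~96 subjects, was determined by how many subjects satisfy all inclusion/exclusion criteria". Matched cohort sizes, entry ages, alpha and sidedness are not stated.

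**Direction, by algebra.** Let E be entry age, X exit age and d(u) the events at age u.
- As written: N0(u) = number with X ≥ u.
- With entry ages: N1(u) = number with E < u ≤ X.
- Curve: S(t) = product over u ≤ t of [1 − d(u)/N(u)].

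Since N0(u) ≥ N1(u) at every age, S0(t) ≥ S1(t), so the median as written is never the earlier one. Under the entry ages assumed below, about 18-19 of 45 boys are under observation at 10.5. One event then should lower the curve by 1/19 = 5.3% to 1/18 = 5.6%. With up to 45 counted, it lowers it by as little as 1/45 = 2.2%.

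**Inputs for size.**
- From the documents: 240 weeks × 7/365.25 = 4.6 years of follow-up; timed tests every 48 weeks; spirometry every 24 weeks; entry at 9-18, event-free.
- Assumed, model A: Weibull event age (shape 4-6, median 13.0 or 13.8 given event-free at 9); entry age truncated normal, SD 2, mean 10.5-11.5 after selection.
- Assumed, model B: normal event age (mean 12, 13 or 14, SD 2.5), 5% dropout per year, 50 versus 50 boys.
- Both: identical hazards in the two cohorts, entry independent of event age apart from the selection, two-sided 0.05.

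**Ambulation medians, model A (years late)**

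| Event dating | As written | Delayed entry |
|---|---|---|
| Exact | 0.4 to 1.3 | within 0.1 |
| Half exact, half at 48-week tests | 0.6 to 1.5 | 0.3 to 0.6 |
| All at 48-week tests | 0.7 to 1.7 | 0.6 to 1.05 |
| Boys within 0.25-0.5 year of the event excluded at entry (stand-in for the 26.4-second cap) | 0.5 to 1.5 | 0.2 to 0.9 |

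**Ambulation medians, model B, exact dating, equal entry ages**

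| True median | As written | Delayed entry |
|---|---|---|
| 12.36 | 13.1 | 12.4-12.6 |
| 13.17 | 13.7 | 13.1-13.3 |
| 14.07 | 14.4-14.5 | 14.0-14.2 |

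That is about 0.4 to 0.8 year late as written.

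**Matched FVC medians.** Model A's approach with 24-week tests and true medians 16-20: 0.1 to 1.9 years late as written, −0.1 to 0.6 with delayed entry. Normal event ages (SD 3, means 16, 18, 20): 1.2, 0.6 and under 0.1 year late. The bias fades when the event falls long after entry.

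**Log-rank false positives, ambulation, model A, 45 versus 75 boys**

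| Mean entry-age gap | As written | Delayed entry |
|---|---|---|
| None | 4-6% | 4-6% |
| About 0.5 year | 6-11% | 4-6% |
| About 1 year | 13-29% | 4-7% (7-9% if all events are found at 48-week tests) |

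At the one-year gap, 98-100% of the as-written rejections favour the older-entering cohort. Model B agrees: at a gap of about 1.3 years, 20-39% reject in that cohort's favour (nominal 2.5% on that side). Varying CINRG follow-up over 2, 7 and 10 years (event-age mean 13) did not change which cohort was favoured.

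**If entry and event ages are correlated.** With correlation 0.4, identical event-age distributions and a gap of about 1 to 1.2 years, the log-rank test as written rejects in 8% and the delayed-entry test in 14-24%. Delayed-entry medians then come out 0.2-0.3 year early (0.5-0.7 at correlation 0.6); those as written stay 0.75-1.1 late.

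**The case against.** The strongest objection is to the remedy. Delayed entry is valid only if entry age and event age are independent apart from the truncation, and that is doubtful here. Study 019 recruits from earlier trials, Study 007 required boys to be ambulatory at its baseline, and CINRG entry is a registry's first visit. If slower progressors join later, delayed entry alone can make the test worse, as the last calculation shows. This stands and shapes the fix.

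Second, the log-rank distortion needs an entry-age gap. With equal ages the test is near nominal, and the SAP tabulates age and allows matching to be revised. That also stands, as far as it goes: revised matching could shrink a gap, but it has no threshold and leaves the risk sets, and so the late medians, unchanged.

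Third, a reader might infer that every ambulation curve in the SAP has this fault. The documents do not settle that. In SAP 5.8.2 the ambulatory restriction is attached to the descriptive summaries, SAP 4 defines boys above 30 seconds at screening, and SAP 5.1 runs analyses overall by default. If such boys entered the stand-alone curve, their screening age would become the event age, which is left censoring with bias of either sign. Protocol 7.2.17 suggests they do not enter, but the SAP does not say so.

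Fourth, part of the delay comes from 48-week testing and the 26.4-second cap. Delayed entry does not remove that part.

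**Conclusion.** The fault is established for SAP 8.2.1: inclusion requires being event-free, and the risk sets ignore when inclusion happened. Under the assumed inputs with exact dating, ambulation medians are about 0.4-1.3 years late even with equal entry ages. Matched FVC medians may be late by far less. The log-rank test is sound with equal entry ages and rejects roughly 13-29% of the time under the null at a gap of about one year. For 5.8.2, 5.9.2 and 5.9.3 the same holds for loss of ambulation only if the curve is limited to boys ambulatory at entry.

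A reader might go further and conclude that the comparison is tilted towards ataluren. The documents do not support that: they give entry ages for neither cohort, so the tilt could run either way or be negligible. The sizes rest on the stated assumptions. The primary endpoint is safety and these analyses are supportive, so this should be fixed but does not undermine the trial's main purpose.

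**What to change.** **In SAP 8.2.1:**
- Use age at study entry (first visit for CINRG) as the delayed-entry time in Kaplan-Meier and in the log-rank or Cox comparison.
- Start compared curves at one pre-specified age with enough boys at risk in each cohort, for example at least 10. Label medians as conditional on being event-free at that age.
- Show entry-age distributions and numbers at risk by age. Report strata that never reach the minimum descriptively. The steroid-no stratum is the likely case, since the ambulation match requires at least 12 months of steroids at entry.
- State the independence assumption and check it, for example with a truncation-adjusted (conditional) Kendall's tau or with entry age as a covariate in the delayed-entry Cox model. Report the analysis without entry ages alongside. If dependence appears, adjust for entry age or treat the comparison as descriptive.

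**In 5.8.2, and in 5.9.2-5.9.3 for loss of ambulation:** state that the curve is limited to boys ambulatory at entry, and apply the same delayed entry.

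**Stand-alone FVC (5.8.5 and 5.9), a secondary point:** a boy already below 1 liter at entry is left-censored, not an event at that age. With 9-30% of boys in that position (assumed), medians as written are off by +0.7, +0.2 and −0.2 to −0.1 year for true medians of 16, 18 and 20. Either restrict to baseline FVC of at least 1 liter together with delayed entry (+0.1 to +0.5), or keep all boys and use an interval-censored (Turnbull) estimator. Restricting without entry ages is worse (+0.5 to +1.9).

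**Cost:** an entry-time option, a start age, one eligibility line and a dependence check. Entry ages are already used for matching, and the SAP already takes the first visit as CINRG baseline. Early risk sets are small: about 18-19 of 45 boys, or 8 of 20, at age 10.5. The gain in root-mean-square error for medians is small at 45 boys (0.4-0.7 versus 0.5-1.0 year) and little or none at 20 (0.6-0.9 versus 0.6-1.1). The report should say that delay from visit spacing and the baseline cap remains.
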